17.1 Subject Compliance

Participants will be telephoned to remind them of a forthcoming visit and to ask them to bring with them their used and unused study medication. Windows of +/- 7 days on follow-up visits should ensure visit attendance; non-attendance for study visits will prompt follow-up by telephone.

Compliance with study medication will be assessed by checking and recording the remaining number of capsules after each visit. Study drug accountability will be assessed and documented by the local pharmacy. The clinical team will also perform a quick review of any returned study medication at each study visit to identify any obvious compliance concerns and address these immediately with the participant.

17.2 Withdrawal of Participants

The study drug must be discontinued if:

- the participant decides they no longer wish to continue
- recommended by the investigator
- the participant loses mental capacity during the study and, in the opinion of the carer/informant would be distressed by the prospect of continuing in the study

Participants have the right to withdraw from the study at any time for any reason (and without stating a reason for withdrawal). The investigator also has the right to withdraw patients from the study drug in the event of inter-current illness, AEs, SAEs, SUSARs, protocol violations, cure, administrative reasons or other reasons.

It is understood by all concerned that an excessive withdrawal rate could render the study uninterpretable; therefore, unnecessary withdrawal of patients should be avoided. Should a patient decide to withdraw from the study, all efforts will be made to report the reason for withdrawal as thoroughly as possible and to conduct an 'end of study' follow-up assessment. Should a patient wish to withdraw from study drug, or be withdrawn from treatment, efforts will be made to continue to obtain follow-up data in line with the study protocol, with the permission of the patient. This is essential for the statistical analysis (intention to treat) and will be made clear in the patient information sheet at the time of initial consent.

Participants who wish to withdraw from study medication will be asked to confirm whether they are still willing to provide the study specific data at the remaining scheduled visits.

If participants agree to any of the above, they will be asked to complete a confirmation of withdrawal form to document their decision.

18. Data Monitoring, Quality Control and Quality Assurance

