15.1 Assessments / Data Collection

Each study visit should last approximately 3 to 3.5 hours for assessment of both the participant and carer/informant. The exception to this is Visit 1 where the number of assessments including the recording of background information will make this the longest visit.

Visit 1: Screening (-14 days +/- 2 days, e.g. days 12-16)

The following procedures and assessments will be carried out at the screening visit:

- 1. Capacity Assessment
- 2. Informed consent for participant and carer informant
- 3. Nomination of back-up spokesperson and/or Personal Consultee
- 4. Checking that the participant fulfils the UK Queen Square Brain Bank Criteria for PD
- 5. Establishing the nature and temporal sequence of onset of cognitive symptoms in relation to parkinsonism (dementia that develops ≤ 1 year of onset of motor symptoms represents an exclusion criterion as the person would be classified as having Dementia with Lewy Bodies under such circumstances)
- 6. ACE-R (must score ≤ 88)
- 7. If screen positive (≤ 88) on ACE-R, Mattis DRS-2 (must have an age- and education-corrected total score of ≤ 8 but ≥ 4 , to define "mild" dementia)
- 8. Beck Depression Inventory: completed by participant. If score ≥ 13 then exclude on the basis of significant depression, which may be a confounder for cognitive assessments.
- 9. Medical history
 - a. such severe motor disability, or participants so impaired in their activities of daily living from other aspects of their PD, as to render it impossible to accurately assess cognitive and neuropsychiatric function and ability to rate BADLS would represent an exclusion criterion
 - b. unstable ongoing medical co-morbidity (would represent an exclusion criterion)
 - c. neurosurgery for PD (e.g. DBS) within 12 months of the screening visit
- 10. Drug history
 - a. concomitant medications (stable dose of antipsychotic agents *are* permitted providing dose has remained unchanged for previous 6 weeks)
 - b. previous exposure to a cholinesterase inhibitor is an exclusion criterion
 - c. known sensitivity to donepezil hydrochloride or the excipients of donepezil hydrochloride or placebo are exclusion criteria
 - d. current or previous exposure to memantine is an exclusion criterion
 - e. current use of a non-selective centrally acting anticholinergic drug for control of motor symptoms is an exclusion criterion

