Note: Assessments 1-7 must be carried out by an independent rater (that is, an investigator who is unaware of the outcome of the other assessments to be performed at this visit, such as recording of adverse events, which could potentially un-blind the assessor). The participant should be requested not to discuss possible adverse events or interim problems with this rater prior to their assessments being performed.

Note: Ensure an adequate rest break is provided during the visit along with refreshments for the patient and the spokesperson.

Visit 7: End of study - 104 weeks (± 7 days)

The following procedures and assessments will be carried out at this visit:

- 1. Mattis DRS-2
- 2. NPI-10 (administered to caregiver/informant)
- 3. BADLS (administered to caregiver/informant)
- 4. Modified ADCS-CGIC interview and scoring
- 5. Montreal Cognitive Assessment (MoCA)
- 6. Parkinson's Disease Cognitive Rating Scale (PD-CRS)
- 7. SCales for Outcomes of PArkinson's disease-cognition (SCOPA-cog) (administered to patient)
- 8. EQ-5D
- 9. DEMQOL and DEMQOL-proxy (latter administered to caregiver/informant)
- 10. Scale of Quality of Life of Caregivers (administered to caregiver/informant)
- 11. UPDRS
- 12. Client Service Receipt Inventory (assessing service use over preceding 6 months) (administered to caregiver/informant)
- 13. Activities-Specific Balance Confidence Scale (ABC)
- 14. Review any adverse events
- 15. Haematological and biochemical tests, as outlined above for visit 5
- 16. Check concomitant medications
- 17. Check study medication returned.

Note: Assessments 1-7 must be carried out by an independent rater (that is, an investigator who is unaware of the outcome of the other assessments to be performed at this visit, such as recording of adverse events, which could potentially un-blind the assessor). The participant should be requested not to discuss possible adverse events or interim problems with this rater prior to their assessments being performed.

Note: Ensure an adequate rest break is provided during the visit along with refreshments for the patient and the spokesperson.

Note: If a participant withdraws prematurely from the study, the end of study visit procedures and assessments should be attempted at the point of withdrawal.

Visit 8: Telephone Call (week 106 ± 2 days)

The purpose of this call is primarily to record any adverse effects that may have occurred in the two weeks after discontinuation of study medication.

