At the end of the study, original questionnaires, case report forms and consent forms will be securely archived for 15 years following publication of the last paper or report from the study, in line with Sponsor policy and NCTU standard operating procedures. This will also allow any queries or concerns about the data, conduct or conclusions of the study to be resolved.

Data sharing

Permission for data sharing with third parties at the end of the study will be sought from all participants, the appropriate Research Ethics Committees and Caldicott Guardians. All data to be shared will be anonymised, with a unique study identifier (for patient or carer as appropriate) allowing linkages between multiple records and files. The quantitative data sets will be fully documented both in terms of internal labelling (eg in 'system' files for commonly used statistical packages such as SPSS and STATA) and external description (data dictionary). These data sets will be prepared during the last 4 months of the study. For the first 24 months after the end of the study, the data will only be available to members of the study team (while papers are being prepared for publication). Thereafter, the quantitative data sets will be made available for independent, external usage. Formal application and registration to use the data will be required.

All efforts should be made to collect all study date for each visit. If a patient is unable to attend a study visits, even with the + 7 days window, due to ill health the following two items should be conducted over the telephone with the care-giver/informant:

BADL NPI-10

16. Statistical Considerations

The primary outcomes, the DRS, NPI-10 and the BADLS, will be assessed at baseline and then at weeks 26, 52, 76 and 104.

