16.1 Statistical Analysis

Analysis will be on the basis of intention to treat. The main statistical challenge in analysing such data is to take into account incomplete data which will be due to a number of factors including the occurrence of side effects or the death of individual participants. Although approximately 50% of patients are expected to discontinue medication prematurely during the study, the actual loss to follow up at 104 weeks is expected to be around 20%, yielding 80% of the original group providing data on the primary outcome measures at 104 weeks. It is likely that those participants who are lost to follow up during the trial may also be people with a tendency to experience poorer outcomes (in terms of the DRS scores) than those who remain in the study.

It is necessary to take into account any difference in dropout rates and the non-randomness of the drop out when comparing functional status between the two treatment groups. This will be done by jointly modelling "survival in the study" and the repeated measures of functional status simultaneously ³³ using software that has been developed as part of an MRC funded programme of work (Grant G0400615; Statistical methodology for longitudinal studies in clinical research; Williamson PR, Diggle PJ and Henderson R). Time to drop-out will be analysed using a Cox proportion hazards model incorporating random effects. Functional outcomes will be modelled using mixed models appropriate for repeated measures. A key feature of each of these models is that within each it is possible to fit a latent variable that can be conceptualised as the patient's propensity to experience poor outcomes (both their likelihood to drop out of the study and their likelihood to have poor DRS scores). It is the inclusion of this latent variable that allows us to adjust our estimates of the treatment effect to allow for the different rates of drop out in each group. Both models are estimated simultaneously; parameter estimates are based on maximising the joint likelihood over both the survival and repeated measures data.

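### The telephone NPI-10 and BADLS interview is limited to visits missed through ill health, so some data on two primary outcomes may be lost avoidably once participants stop trial drug

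*Protocol*

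**What the plan says.** - **After stopping drug (17.2).** The general commitment is that "efforts will be made to continue to obtain follow-up data in line with the study protocol, with the permission of the patient". The only question printed is put to participants who wish to come off study medication, who are "asked to confirm whether they are still willing to provide the study specific data at the remaining scheduled visits". The section then says: "If participants agree to any of the above, they will be asked to complete a confirmation of withdrawal form to document their decision". The withdrawal form is Appendix H, which is not shown.
- **Visit burden (15.1).** "Each study visit should last approximately 3 to 3.5 hours for assessment of both the participant and carer/informant".
- **Telephone outcome collection (end of 15.3).** All efforts are to be made to collect the data at each visit. If a patient cannot attend even within the window, "due to ill health the following two items should be conducted over the telephone with the care-giver/informant". The two items are BADLS and NPI-10.
- **Missed visits (17.1).** "non-attendance for study visits will prompt follow-up by telephone". The section does not say that outcomes are collected on that call.
- **Withdrawal from the study (15.1, Visit 7).** "If a participant withdraws prematurely from the study, the end of study visit procedures and assessments should be attempted at the point of withdrawal".
- **What the design relies on (16.1, 16.2).** Section 16.1 states that "approximately 50% of patients are expected to discontinue medication prematurely during the study" and puts loss at week 104 at about 20%. It adds that those lost are likely to be people with poorer outcomes. Section 16.2 hopes to reach 80% retention by encouraging those who stop drug to keep to the follow-up schedule.

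**The concern.** NPI-10 and BADLS are given by the carer, and 15.3 already accepts both by telephone. Nothing in the protocol explains why such a rating is usable when the participant is too ill to attend but not when the participant declines a long visit, has moved or has no transport. Followed as written, the plan has no stated way to obtain later NPI-10 and BADLS scores from this second group.

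What is at stake is mainly the kind of missing data, and only secondarily its amount. Section 16.1 names side effects among the causes of incomplete data and expects dropout to be non-random and possibly different between arms. The joint model is there to adjust for that, but its adjustment rests on assumptions about data nobody observed. Scores that a call to the carer could have supplied are better observed than modelled.

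**Working it through.** **1. The plan's own figure.** Inputs from 16.2: two-sided 5%, 90% power, 1:1, SD 13.5 (DRS) and 12.0 (NPI-10), differences 4.4 and 3.9, loss 20%. Per-arm n = 2 × (1.960 + 1.282)² × (SD/difference)².
- DRS: 4.4/13.5 = 0.326, n = 198, power at 200 per arm 90.3%.
- NPI-10: 3.9/12.0 = 0.325, n = 199, power at 200 per arm 90.1%.
- Recruitment: 200/(1 − 0.20) = 250 per arm, 500 in total.

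The stated sample size reproduces.

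**2. What 80% retention asks of those who stop drug.** 500 × 0.50 = 250 stop. Retaining 400 when all 250 still on drug stay needs 400 − 250 = 150 of the 250 who stop, or 60%. If all loss falls among those who stop, 100 of 250 (40%) are lost.

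**3. Effect of a wider telephone fallback on NPI-10 and BADLS.** The documents give no recovery rate, so it is an assumption. Power uses effect size 0.325, which 16.2 applies to both scales. The detectable NPI-10 difference is 3.9 × √(200/n per arm).

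| Share of the 100 losses recovered | Retention | n per arm | Power | Detectable NPI-10 difference |
|---|---|---|---|---|
| 0% | 80% | 200 | 90.1% | 3.90 |
| 25% | 85% | 212.5 | 91.8% | 3.78 |
| 50% | 90% | 225 | 93.1% | 3.68 |

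**4. If retention falls short of plan.** Suppose 60% of those who stop are lost: 0.50 × 0.60 = 30% lost, 70% retained, 175 per arm, power 86.0%. Recovering half of those losses gives 85% retained and power 91.8%.

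**5. Which routes exist, by reason for missing a visit after stopping drug.**
- *Ill health, including an adverse event:* covered by 15.3, which does not require the participant to be on drug.
- *Declines, cannot travel or has moved:* the 17.1 call is made, but collecting outcomes on it is not stated.
- *Leaves the study:* one assessment is attempted at withdrawal. It does not supply the later scheduled values.
- *DRS-2 in any of these cases:* not among the telephone items, so a wider fallback would not recover it.

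**The case against.** Several stronger readings are tempting, and the documents do not support them.

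- **That people who stop drug are offered full visits or nothing.** Section 17.2 also commits to efforts to continue follow-up, 17.1 prompts a call after any non-attendance, and the reference in 17.2 to agreeing to any of several things suggests more than one choice. Appendix H may list options. What remains is that 17.2 prints one question and 15.3 ties the outcome call to ill health.
- **That all three primary outcomes are lost for these participants.** Scores from earlier visits and from the withdrawal assessment still enter the joint model. Only later scheduled values are missing.
- **That the trial is underpowered.** The 20% loss is already allowed for, and power at the planned retention is about 90%.
- **That the telephone interview escapes blinding.** Section 14 requires an independent assessor for these scales at each visit, and nothing exempts the call. But 15.3 does not name the caller, and illness is what triggers the call, so a clarification is worth adding.

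There is also a fair defence of the current rule. Asking first for scheduled visits protects DRS-2, and also EQ-5D, DEMQOL and CSRI, which feed the economic analysis. An open offer of telephone follow-up could draw away people who would have attended. This stands, and it limits the remedy to a fallback. It does not explain why the existing fallback stops at ill health.

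**Conclusion.** The point holds as a gap in data collection. The telephone route for NPI-10 and BADLS covers ill health only, and 17.2 prints no fallback for people who stop drug and miss later visits for other reasons. Some data on two of the three primary outcomes may therefore be lost avoidably, in a group where the protocol itself expects loss to be informative.

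The gain in precision is modest: under the assumed 25% to 50% recovery, about 1.6 to 3.0 percentage points of power. Even that range may be generous, because the 100 losses include deaths and full withdrawals of consent that no call can recover, and the number of willing carers is unknown. The main benefit is less informative missingness, which cannot be quantified from the document. This is a cheap improvement and not a flaw that undermines the design.

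**What to change.** 1. **Section 15.3:** replace the ill-health condition with *for any reason, including after stopping study medication, with the participant's permission*. State that the call is used only after the scheduled visit has been sought and then declined or missed.
2. **Section 17.2:** refer to this fallback, and check that the withdrawal form agrees with it.
3. **Rater:** state that the independent rater makes the call and is not told why the visit was missed.
4. **CRF:** record the mode of assessment for NPI-10 and BADLS at each time point.

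The cost is protocol wording, a check of the withdrawal form and one CRF field. The downsides are a few more telephone ratings, mixed assessment modes that may differ by arm, and a small risk that some participants choose the call over a visit. That risk is why the full visit should be asked for first, and why a menu presenting the call as an equal alternative is not proposed.

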18.1 Discontinuation Rules

The trial may be prematurely discontinued on the basis of new safety information, or for other reasons given by the Data Monitoring and Ethics Committee / Trial Steering Committee, sponsor, regulatory authority or ethics committee concerned.

Following 12 months of recruitment, initial rates of recruitment will be used to project total recruitment to ensure sufficient participants to power the trial. The Trial Steering Committee (TSC) will advise on whether to continue or discontinue the study and make a recommendation to the sponsor and funder. If the study is prematurely discontinued, active participants will be informed and no further participant data will be collected.

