19.3 Protocol Specifications

For purposes of this protocol

- All non-serious adverse reactions will be recorded at visits 3-7.
- Any serious adverse events will be recorded throughout the duration of the trial until 2 weeks after the trial medication is stopped.
- Serious adverse events exclude any pre-planned hospitalisations not associated with clinical deterioration.
- Serious adverse events exclude routine treatment or monitoring of the studied indication, not associated with any deterioration in condition.
- Serious adverse events exclude elective or scheduled treatment for pre-existing conditions that did not worsen during the study.

19.4 Recording and Reporting Serious Adverse Events or Reactions:

All adverse events should be reported. Depending on the nature of the event, the reporting procedures below should be followed. Any questions concerning adverse event reporting should be directed to the Chief Investigator or MUSTARDD-PD Trial Manager in the first instance. Figure 1 summarises the reporting procedures.

Adverse Event (including Adverse Reaction): All non-serious adverse events / reactions during drug treatment will be reported on the study CRF and sent to Newcastle Clinical Trials Unit within 2 weeks of the form being due. Severity of AEs will be graded on a three-point scale (mild, moderate, or severe – see above). Relation of the AE to the treatment should be assessed by the investigator at site. The individual investigator at each site will be responsible for managing all adverse events / reactions according to local protocols as the study drug is licensed for use in other indications.

Serious Adverse Event / Reaction (SAE/SAR, including SUSARs): All SAEs, SARs and SUSARs during drug treatment will be reported to the Chief Investigator within 24 hours of learning of their occurrence. The initial report can be made by telephone, fax or e-mail. In the case of incomplete information at the time of initial reporting, all appropriate information should be provided as follow-up as soon as this becomes available. Relationship of the SAE to the treatment should be assessed by the investigator at site, as should the expected or unexpected nature of any serious adverse reactions.

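### Section 18.1 ends all data collection if the trial stops early, which conflicts with the two-week post-medication SAE recording in 19.3 and the purpose of the Visit 8 call

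*Protocol*

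**What the plan says.** Section 18.1 (Discontinuation Rules) opens with the grounds for stopping: "The trial may be prematurely discontinued on the basis of new safety information", or for other reasons given by the oversight committees, sponsor, regulator or ethics committee. It then schedules a feasibility review: "Following 12 months of recruitment, initial rates of recruitment will be used to project total recruitment". On that basis the Trial Steering Committee advises whether to go on. The section closes with the rule at issue: "If the study is prematurely discontinued, active participants will be informed and no further participant data will be collected".

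Section 19.3 sets the safety window: "Any serious adverse events will be recorded throughout the duration of the trial until 2 weeks after the trial medication is stopped". In section 15.1, Visit 8 is a telephone call placed two weeks after the week-104 visit, and its aim is stated: "The purpose of this call is primarily to record any adverse effects that may have occurred in the two weeks after discontinuation of study medication". Section 19.4 asks for further information on incompletely reported SAEs once it becomes available, and section 19.5.2 has pregnancies followed to their outcome.

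For individuals who leave, section 15.1 says: "If a participant withdraws prematurely from the study, the end of study visit procedures and assessments should be attempted at the point of withdrawal". Section 17.2 adds, "Should a patient decide to withdraw from the study, all efforts will be made to report the reason for withdrawal", and asks for an end-of-study assessment as well. For those who stop study drug only, 17.2 seeks continued follow-up and calls it essential to the intention-to-treat analysis.

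**The concern.** The rule in 18.1 is absolute. It separates neither safety data from outcome data nor a stop for slow recruitment from a stop for a safety signal. Read literally, it switches off the two-week post-medication safety window for every participant on drug when the trial closes. That window is most needed when the reason for closing is new safety information. Follow-up of SAEs already reported in part, and of pregnancies, would lapse as well.

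There is a second, lesser cost. Primary outcomes are measured about every 26 weeks. Without a closing assessment, an active participant contributes no outcome data after the last scheduled visit, and a participant not yet at week 26 contributes a baseline only. These gaps arise because the data are never collected, so no later analysis plan can repair them.

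**Working it through.** **1. The plan's own figures, for completeness.** Section 16.2 gives 200 completers per group, 90% power, two-sided 5%, DRS difference 4.4 with SD 13.5, and NPI-10 difference 3.9 with SD 12.0. With n per group = 2(1.960 + 1.282)² / (difference/SD)²:
- DRS: 4.4/13.5 = 0.326, n = 198, power at 200 per group 90.3%.
- NPI-10: 3.9/12.0 = 0.325, n = 199, power at 200 per group 90.1%.
- Recruitment: 400/(1 − 0.20) = 500.

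All of these reproduce. The point does not touch them.

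**2. The safety texts side by side.**

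| Provision | Trigger | Instruction | Compatible with 18.1 at trial closure? |
|---|---|---|---|
| 19.3, SAE recording | Trial medication stopped, whatever the reason | Record for 2 more weeks | No |
| 15.1, Visit 8 | Purpose: the 2 weeks after stopping medication; timing: week 106 | Record adverse effects | Not with its purpose; its fixed timing does not cover an early stop |
| 19.4, incomplete SAE reports | SAE already reported | Supply follow-up information | No exception in 18.1 |
| 19.5.2, pregnancy | Pregnancy during participation | Follow to outcome | No exception in 18.1 |
| 15.1 and 17.2, closing assessment | An individual withdraws | Attempt end-of-study assessment | Yes in wording; different in principle |

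The conflict rests on 19.3. Its window starts when medication stops, and trial closure is one way in which that happens. Visit 8 supports it through its stated purpose.

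**3. Outcome data not obtained.** Inputs: primary outcome visits at baseline and weeks 26, 52, 76 and 104 (section 16), and the recruitment review after 12 months (18.1). Assumptions, not in the protocol: uniform recruitment up to the stop, no dropout, visits exactly on schedule. For a stop T weeks after the first randomisation, the share of all randomised participants with baseline only is 26/T:
- T = 52: 26/52 = 50%
- T = 78: 26/78 = 33%
- T = 104: 26/104 = 25%
- T = 130: 26/130 = 20%

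The mean time since the last scheduled visit, among those still active, is the sum of (interval length)²/2 over the visit intervals, divided by the follow-up range:
- T = 52: (338 + 338)/52 = 13.0 weeks
- T = 78: (338 + 338 + 288 + 2)/78 = 12.4 weeks
- T = 104 or 130: (338 + 338 + 288 + 392)/104 = 13.0 weeks

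A closing measurement would have a use, because section 16.1 plans a repeated-measures model fitted jointly with time to dropout. The ADCS-CGIC is not scored at baseline, so a baseline-only participant also adds nothing to the comparison of cognitive scales against it (16.4).

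**The case against.** The strongest defence is that 19.3 is a specific pharmacovigilance rule that governs safety reporting whatever happens, so that 18.1 refers only to trial assessments. The sentence also sits in the paragraph on recruitment, apart from the one that mentions safety. Neither argument succeeds. Nothing in the protocol defines participant data so as to leave out safety data, and the sentence speaks of premature discontinuation in general, which is the term used for stopping on safety grounds.

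Other parts of the defence stand, and they rule out stronger readings that a reader might infer:
- *That 18.1 contradicts the end-of-study assessment.* Sections 15.1 and 17.2 trigger it when an individual withdraws, and only as a best effort. A site can follow them and 18.1 together.
- *That outcomes are thrown away.* The rule stops new collection. It removes nothing already recorded.
- *That everyone stops drug at the same moment.* Section 18.1 gives no timing for stopping medication or for an orderly close-down.
- *That the rule costs the trial its week-104 results at an early stop.* Nobody can have reached week 104 at 12 months under any closure rule. A closing assessment at that point would not supply the 24-month outcome either.
- *That an early-closure call is already scheduled.* Visit 8 is fixed at week 106, so its timing would need rewording.

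It is also fair to say that ending outcome assessments in a trial closed as infeasible is a defensible choice, given the length of the visits. That argument does not extend to safety recording.

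**Conclusion.** The point holds as a conflict between 18.1 and 19.3, supported by the purpose of Visit 8 and made wider by the lack of any exception for SAE and pregnancy follow-up. It rests on the text alone and needs no assumption. If 18.1 is followed literally, the post-medication safety window is lost for all participants on drug at closure.

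On outcome data, 18.1 is out of line with how the protocol treats an individual withdrawal but does not contradict its wording. The baseline-only share is about 50% at the earliest scheduled decision point and falls to about 20% for a stop at 130 weeks, with a mean unobserved gap of about 12 to 13 weeks. The 50% should not be read as a general figure: it depends on uniform recruitment, no dropout and a stop at 12 months. Type 1 error, power and sample size are unaffected. The sentence should be corrected. It matters only if the trial closes early, but by then the safety data it blocks could no longer be collected.

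**What to change.** Reconcile the passages by amending the last sentence of 18.1, for example: *On premature closure of the trial, active participants are informed. Before data collection ends, SAE recording under section 19.3 is completed for the two weeks after each participant's medication stops, the Visit 8 safety call is made at the end of that period, and any outstanding SAE and pregnancy follow-up is completed. Where the participant agrees, the Visit 7 assessments, or at least the DRS-2, NPI-10 and BADLS, are attempted at closure.*

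Visit 8 in 15.1 and in the schedule (15.2) needs a matching note that, for an early stop, the call is timed from the stop of medication rather than at week 106.

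The cost is an amendment of a few lines that relies on existing procedures, then one call per active participant at closure and, optionally, one visit that 15.1 puts at about 3 to 3.5 hours for participant and carer. That visit is a real burden in a trial that has closed, which is why it should be optional and may be cut to the three primary outcomes. The safety elements should not be optional.
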